1.2. Methadone providers

Methadone providers will conduct the study interventions under the clinical supervision of the study master counselors. All methadone providers have been trained on basic addiction medicine and will receive further training to deliver the study interventions. We will conduct in-depth interviews with them before and after the intervention phase.

Randomization and Interventions

An investigator will stratify participants by HIV status and randomize them into two frontline interventions using REDCap, as shown in Figure 1. She will send the allocation results to the site research assistants who will then inform providers at the study clinics. This is an open label study so unblinding does not occur. Participants and their counselors, research assistants and data managers are aware of participants' assignment of intervention. Participants will receive two individual sessions of motivational interviewing with their counselors before they get into the frontline interventions and, in Week 13, before the adaptive strategies start. These sessions would boost participants' motivation for intervention and provide them with greater details of the upcoming intervention activities.

Two frontline interventions (Weeks 1-12)

- High intensity: Participants in this arm receive contingency management with the escalating-and-reset schedule throughout 12 weeks. This schedule means participants receive increasing rewards for consecutive negative UDS but if the streak of negative UDS is broken,

their rewards return to the starting level. The maximal reward value over 12 weeks is \$150 USD, equivalent to the average monthly income of our participants.

- Low intensity: Participants in this arm receive contingency management for the first six weeks with the maximal reward value of \$40 USD. For the last six weeks, they attend weekly group education sessions. The topics of group education include 1) Addiction mechanism, 2) Road to recovery, 3) Coping with triggers, 4) Boredom, 5) Building trust and 6) Relapse prevention.

Participants with four consecutive UDS negative with methamphetamine in weeks 11 and 12 are considered to be responsive to frontline interventions. Others are considered non-responsive. Responders to frontline interventions are placed in the maintenance treatment arm. Non-responders are randomized to either enhanced treatment 1 or 2.

Three adaptive strategies (Weeks 14-25)

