- Maintenance treatment: Participants receive two daily automatic unidirectional scripted SMS reminders plus one weekly self-monitoring assessment message over 12 weeks.
- Enhanced treatment 1: Participants attend 12 weekly Matrix group counseling sessions facilitated by the clinic counselors. Our Matrix intervention has the same structure, albeit it is shorter than the original 24-sessions model.
- Enhanced treatment 2: Participants receive the same Matrix intervention plus contingency management over 12 weeks.

Definition of effectiveness measures

Effectiveness measures will be assessed at 13-, 26- and 49 weeks after the first week of frontline interventions and throughout the interventions. Primary outcomes include: (1) increase in HIV viral suppression for HIV-positive participants at 26- and 49-weeks; (2) reduction in HIV risk behaviors for both HIV-positive and HIV-negative participants at 26- and 49-weeks; and (3) reduction in methamphetamine use at 13-, 26- and 49-weeks measured by UDS (point abstinence) and self-report (continuous abstinence and longest period). Secondary outcomes include: (1) adherence to antiretroviral treatment for HIV-positive participants; 2) frequency of HIV testing for HIV-negative participants; 3) heroin use with UDS; 4) opioid overdose; and, 5) quality of life.

To acquire the primary and secondary outcomes, we will assess for the following:

- HIV viral load test. At baseline, Week 13, Week 26 and Week 49, we send blood samples of HIV-positive participants to laboratories at Bach Mai Hospital in Hanoi and HCMC University of Medicine and Pharmacy Hospital in HCMC for viral load quantification.

- Drug screening. We use an FDA-approved Multi-Drug Rapid Test Panel to detect methamphetamine, opioid, and cannabis in urine twice a week throughout the intervention period and at Week 49.
- Methadone and HIV treatment. We extract methadone and HIV treatment data from participants' medical charts. Variables of interest include length of treatment, treatment regimen, medication dose and treatment adherence.

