necessary; two counselors will run motivational interviewing, group education sessions and Matrix meetings; the nurse will collect urine twice a week and conduct contingency management based on the UDS results. Before the start of the intervention, to ensure the accuracy, integrity and fidelity to the EBIs, all intervention staff at methadone clinics will (1) receive didactic training on the theory behind the approach; (2) evaluate their comprehension of the concepts within and behind the approach; (3) watch a video of a Master Behavioral Counselor conducting intervention sessions and discuss the details of the session, and (4) conduct at least two pilot intervention instances. All intervention sessions, except contingency management, will be audio recorded, transcribed, and coded to ensure intervention fidelity. Intervention staff who have lower levels of intervention integrity or who have significant drift will be provided detailed feedback and supervision until there is parity with other staff.

Sample size determination

Sample sizes were chosen to compare primary outcomes based on first-stage randomization into one of two groups: high intensity or low intensity frontline interventions. Sample size calculations are conducted in PASS 2008 (65) for a two-group comparison of binary outcomes, a power of 80%, a 5% alpha level, and a conservative attrition rate of 20%. Using estimates from our prior work, we anticipate base rates of 80% to 90% for substance use and 60% to 70% for viral suppression. Based on these assumptions and a proposed sample of 200 HIV-positive participants (with 100 participants per group), we can detect randomization group differences of 20% or more for binary outcomes, such as substance use and viral load suppression. We can detect even smaller group differences for substance use outcomes in the proposed sample of 400 HIV-negative participants and the combined sample of HIV-positive and negative participants. If estimated outcome probabilities are similar between first-stage randomization groups at 12 weeks, we will pool 12-week results for even greater power in evaluating second-stage randomization differences.

Table 1. Assessment schedule

Assessments	Baseline	Week 13	Week 26	Week 49
Sociodemographic characteristics	X			X
Drug use history	X		X	X
Current drug use	X		X	X
Amphetamine use behaviors				
Amphetamine Cessation Symptom Assessment (ACSA)				

Tobacco smoking	X		X	X
Alcohol use	X		X	X
AUDIT-C				

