We will use a time-varying mixed-effects model that will be fitted to the participants' common outcome measures over time. The unadjusted model will include indicators of first-stage and second-stage intervention conditions, time of the assessment (baseline, 13-, 26-, and 49-weeks), and intervention indicators-by-time interaction terms. An additional interaction term of the two intervention indicators will be included to account for any interaction effect between the first and the second stage interventions. The adjusted model will include patients' socio-demographic characteristics, drug use history, HIV-serostatus, and location as fixed effects. The mixed-effects models will include a participant-level random effect to account for repeated observations of each participant, as well as a clinic-level random effect to account for the nested nature within the clinics. We will conduct subgroup analyses among HIV-positive and HIV-negative participants. For the HIV-positive subgroup, the specific outcomes of interest include 1) HIV viral load suppression, and 2) adherence to antiretroviral treatment; and specific outcomes for HIV-negative subgroup include 1) frequency of HIV testing and 2) HIV seroconversion. Substance use will be the common outcomes in models including participants of both HIV statuses.

To assess cost-effectiveness

We will calculate Cost Effectiveness Ratios (CER) for each of the intermediate and final outcomes. The CER is in the broadest terms the difference in per capita costs of administering one intervention (C1-C2) relative to a second, divided by the difference in outcomes between the two interventions (O1-O2):

$$CER = \frac{C1 - C2}{O1 - O2}$$

For example, calculating the CER for adding contingency management to Matrix for non-responders would yield a CER equation. In calculating the CER of high vs. low intensity contingency management at the first randomization stage, the entire range of subsequent costs will be included. Costs of delivering the interventions will be derived from clinic records of time and other inputs, as well as incentive payments, thus providing an estimate of CER from the medical system perspective. We will also evaluate CERs from a societal perspective, using a broad definition of costs, including the social costs of incarceration.

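### The enhanced 2 v enhanced 1 contrast has no covariate summarising the frontline urine series, so some precision is lost; the randomised contrast is not biased

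*Combined protocol and SAP*

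**What the plan says.** Under Randomization and Interventions, a participant whose four tests in Weeks 11 and 12 are all negative for methamphetamine is a responder, and everyone else is a non-responder. "Non-responders are randomized to either enhanced treatment 1 or 2". Under Definition of effectiveness measures, drug screening is done "in urine twice a week throughout the intervention period and at Week 49", and point abstinence by urine is an outcome at Weeks 13, 26 and 49.

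Data analysis (To assess effectiveness) describes one mixed model for all participants. It has indicators for first-stage and second-stage condition, their interaction, time (baseline and Weeks 13, 26 and 49), condition-by-time terms, and random effects for participant and clinic. The adjusted version adds socio-demographic characteristics, "drug use history, HIV-serostatus, and location as fixed effects". No summary of the frontline urine series is listed. The section does not say which value of drug use history is meant, and Table 1 collects it at baseline, Week 26 and Week 49.

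**The concern.** The rule for non-response puts very different people in one group: a participant with a single late positive is re-randomised alongside one who was positive on every test. The series that separates them is complete before the second randomisation and is already collected. The model reaches it through at most one binary Week 13 result.

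Even that result is uncertain. Week 13 falls between the frontline phase (Weeks 1-12) and the adaptive phase (Weeks 14-25), and Table 1 schedules urine during the intervention and at Week 49, although the outcome definition names Week 13.

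The contrast belongs to Aim 1, but the sample size was set on the first stage and no second-stage power or detectable difference is given. Challenges and modifications says at least half the sample must reach the adaptive phase for adequate power, whereas 38% of pilot participants were non-responders. Precision available from existing data is therefore worth having, and a covariate named in advance cannot be chosen after the results are seen.

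**Working it through.** **1. The plan's own figure.** Sample size determination sets "a power of 80%, a 5% alpha level, and a conservative attrition rate of 20" per cent, "for a two-group comparison of binary outcomes". It says "we anticipate base rates of 80% to 90% for substance use and 60% to 70% for viral suppression". With "200 HIV-positive participants (with 100 participants per group", it states that "we can detect randomization group differences of 20% or more for binary outcomes". Sidedness is not given; I assume two-sided.

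n per arm = [1.960·√(2·p̄·(1−p̄)) + 0.842·√(p1(1−p1) + p2(1−p2))]² / (p1−p2)²

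For 80% v 60%: (1.960 × 0.648 + 0.842 × 0.632)² / 0.04 = 82 per arm. Evaluable: 100 × 0.8 = 80 per arm, which gives 79.4% power and a detectable difference of 20.2 points. The stated figure reproduces. It concerns the first stage only.

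**2. Size of the second stage.** The allocation ratio is not stated; I assume 1:1, with 20% attrition.
- At 50% non-response: 600 × 0.50 = 300, 150 per arm, 120 evaluable.
- At 38% (the pilot): 600 × 0.38 = 228, 114 per arm, 91.2 evaluable.

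**3. Number of prior tests.** 2 × 12 = 24 scheduled. This is the schedule, not what each person will have.

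**4. What the series could add.** The documents give no association, so this step rests on a simulation. Each participant has a propensity to test positive, normal on the logit scale with an assumed SD. The 24 frontline tests are drawn from it, non-responders are those without four negatives at the end, and about 50% are non-responders. A later test is drawn from a propensity whose correlation with the frontline one (persistence) is 0.7 or 1.0. R² is from a linear model of the later test among non-responders. R²a uses baseline urine and the last frontline test, as a stand-in for Week 13. R²b uses baseline urine and the mean of all 24. The added variance reduction is 1 − (1−R²b)/(1−R²a).

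| SD | Persistence | R²a | R²b | Added reduction |
|---|---|---|---|---|
| 1.0 | 0.7 | 0.010 | 0.042 | 3.2% |
| 1.0 | 1.0 | 0.020 | 0.094 | 7.6% |
| 1.5 | 0.7 | 0.025 | 0.080 | 5.6% |
| 1.5 | 1.0 | 0.060 | 0.188 | 13.6% |
| 2.0 | 0.7 | 0.040 | 0.105 | 6.8% |
| 2.0 | 1.0 | 0.104 | 0.265 | 18.0% |

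With Week 13 urine and baseline as the comparator and non-response at 38% to 50%, the range is roughly 2% to 15%. I use that range, because it is closest to the planned model. Outside these SDs the table's method gives 0.6% (SD 0.5, persistence 0.7) to 22.8% (SD 3, persistence 1.0).

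**5. Effect on power.** With R the added reduction, power = Φ(2.802/√(1−R) − 1.960).
- R = 0.02: Φ(2.830 − 1.960) = 80.8%.
- R = 0.15: Φ(3.039 − 1.960) = 86.0%.

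**6. Effect on the detectable difference.** Effective n per arm = n/(1−R), using the step 1 formula at 80% power and an 80% positive rate in the comparator arm.

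| Evaluable per arm | R = 0 | R = 0.02 | R = 0.15 |
|---|---|---|---|
| 120 | 16.2 points | 16.0 (n = 122.4) | 14.8 (n = 141.2) |
| 91.2 | 18.8 points | 18.6 (n = 93.1) | 17.2 (n = 107.3) |

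**7. A limit of the simulation.** In the step 4 table, 24% to 42% of non-responders test positive later, well below the 80% to 90% substance use that the plan anticipates. When later positivity is set that high, the added reduction falls to 12% or less, so the lower part of the range is the more likely.

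**The case against.** The strongest reply is that nothing is wrong with the planned contrast. Enhanced 1 v enhanced 2 is randomised, so it is unbiased without this covariate, and ordinary intervals already allow for chance imbalance. That stands, and it makes this a point about efficiency.

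The model also holds more than enrolment data. The frontline arm, its interaction with the second-stage arm and a Week 13 outcome are in it, and the last four frontline tests decide who is re-randomised. A reader might infer that the contrast adjusts only for pre-enrolment characteristics, or ignores the frontline urines altogether. The documents do not support either reading. The entry rule, however, selects the group and does not adjust within it, and one binary result carries less than the series.

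A reader might also infer that the frontline results strongly predict the later outcome. No figure in the documents shows this. Restriction to non-responders narrows the range, and treatment changes between the two periods. Larger gains, such as an 11% to 27% cut in variance, arise only when the comparator is a model with no adjustment, which is not the plan.

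Finally, no gain has been shown for viral suppression or HIV risk behaviours. That limits the proposal to methamphetamine-use outcomes. The possible pooling of 12-week results in Sample size determination is conditional on similar frontline arms and is not covariate adjustment, so it does not fill the gap.

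**Conclusion.** The point holds as a modest, low-cost gain in precision for one contrast. The adjusted model names no summary of up to 24 scheduled results that precede the second randomisation. The expected benefit beyond baseline and Week 13 urine is a variance reduction of roughly 2% to 15%, which takes 80% power to about 81% to 86%. It rests on assumed SDs of 1 to 2, persistence of 0.7 to 1.0, 1:1 allocation, 20% attrition and a linear model on the risk-difference scale. The gain could be negligible if use in the frontline phase says little about use later.

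**What to change.** In Data analysis (To assess effectiveness), add that for enhanced 2 v enhanced 1 on methamphetamine-use outcomes, estimated among re-randomised participants:
- the share of methamphetamine-negative tests among those provided in Weeks 1-12, together with the number of tests provided, is a fixed covariate;
- the frontline arm stays in the model, as already planned;
- drug use history means the baseline value, since the Week 26 and Week 49 values come after the second randomisation.

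State that the share is not used in the high v low intensity contrast, where it is measured after randomisation and may carry part of the effect. Say also which tests count when a frontline phase is interrupted or restarted under the COVID-19 response plan, and how a participant with no tests is handled.

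The cost is a few sentences in the plan and one extra covariate with its test count. The data are already collected, and the gain may be small.

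### A single participant-level random effect, if fitted as a random intercept with model-based standard errors, makes tests of change from baseline to week 49 too liberal when within-person correlation fades with time

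*Combined protocol and SAP*

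**What the plan says.** The model is described in the protocol under Data analysis, To assess effectiveness: "We will use a time-varying mixed-effects model that will be fitted to the participants' common outcome measures over time". Its fixed effects are the first- and second-stage intervention indicators, their mutual interaction, and "time of the assessment (baseline, 13-, 26-, and 49-weeks), and intervention indicators-by-time interaction terms". Baseline is therefore one of the time levels. On dependence within a person the text says: "The mixed-effects models will include a participant-level random effect to account for repeated observations of each participant". A second random effect covers clinic.

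The section does not say whether the participant effect is an intercept or includes a slope. It gives no residual covariance, link function or standard-error method. It also does not say whether effectiveness is judged by an arm difference at a visit or by an arm difference in change from baseline.

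Under Definition of effectiveness measures, "Effectiveness measures will be assessed at 13-, 26- and 49 weeks after the first week of frontline interventions". Viral suppression and HIV risk behaviours are primary at weeks 26 and 49. Methamphetamine use is primary at weeks 13, 26 and 49. Table 1 schedules viral load at all four visits, current drug use at baseline, week 26 and week 49, and quality of life at baseline and week 49 only.

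**The concern.** A random intercept with independent residuals makes every pair of visits equally correlated (on the latent scale for a binary outcome). Baseline and week 49 are then treated as being as alike as baseline and week 13. Correlation in repeated drug-use, viral-load or symptom data commonly fades with time, and here the intervention also changes after week 13.

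The intervention-by-time terms compare arms on change from baseline, and the standard error of a change depends directly on the correlation between the two visits. The primary outcomes are worded as increases and reductions, so these terms are a natural choice for the primary test. If the model overstates the correlation between baseline and week 49, it understates the standard error of that change. The last primary time point then yields too many false positives.

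**Working it through.** **The plan's own figure.** Under Sample size determination, "we can detect randomization group differences of 20% or more for binary outcomes", from a "proposed sample of 200 HIV-positive participants (with 100 participants per group"). Inputs from that section are 80% power, 5% alpha (two-sided assumed) and 20% attrition. For 80% v 60%:

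n = [1.96√(2 × 0.7 × 0.3) + 0.8416√(0.8 × 0.2 + 0.6 × 0.4)]² / 0.2² = 81.2, so 82 evaluable per arm.

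Then 82/0.8 = 102.5, so 103 enrolled against 100 stated. Power with 80 evaluable per arm is 79.4%. The figure reproduces to within 3%. It is a two-proportion comparison with no correlation input, so this point does not change the sample size.

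**Formula.** Take two arms of n, saturated arm-by-visit means, equal variance σ² at each visit and complete data. The fitted common correlation is then r̄, the mean of all pairwise correlations.

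- Arm difference in change from baseline to visit t: the model variance is 4σ²(1 − r̄)/n and the true variance is 4σ²(1 − ρ₀ₜ)/n. The ratio of model to true standard error is √[(1 − r̄)/(1 − ρ₀ₜ)].
- Arm difference at visit t: both variances are 2σ²/n, so the ratio is 1.00.
- True type I error of a nominal 5% test: 2[1 − Φ(1.96 × ratio)].

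**Assumption.** The documents give no correlations. I assume exponential decay, with ρ per 13 weeks of 0.5, 0.7 or 0.9.

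**Worked case, ρ = 0.7, visits 0, 13, 26, 49.** The six correlations are 0.700, 0.490, 0.261 (with baseline), 0.700, 0.372 and 0.532. Their mean is 3.055/6 = 0.509. At week 49 the ratio is √(0.491/0.739) = 0.81, and the type I error is 11.0%.

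**Four visits, change from baseline: ratio (type I error)**

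| ρ per 13 weeks | r̄ | Week 13 | Week 26 | Week 49 |
|---|---|---|---|---|
| 0.5 | 0.294 | 1.19 (2.0%) | 0.97 (5.7%) | 0.87 (8.7%) |
| 0.7 | 0.509 | 1.28 (1.2%) | 0.98 (5.5%) | 0.81 (11.0%) |
| 0.9 | 0.810 | 1.38 (0.7%) | 1.00 (5.0%) | 0.76 (13.5%) |

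**Three visits (0, 26, 49).** r̄ is 0.206, 0.428 and 0.771. The week-49 ratios are 0.93, 0.88 and 0.84, with type I error 7.0%, 8.5% and 10.1%. The week-26 ratios are 1.03 to 1.10.

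**Two visits (0, 49).** r̄ equals ρ₀ₜ, so the ratio is 1.00.

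**Equal true correlation.** All ratios are 1.00.

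**Weak baseline correlation.** Take 0.20, 0.15 and 0.10 with baseline, and 0.7 decay among later visits. Then r̄ = (0.20 + 0.15 + 0.10 + 0.700 + 0.372 + 0.532)/6 = 0.342. The ratios are √(0.658/0.80) = 0.91, √(0.658/0.85) = 0.88 and √(0.658/0.90) = 0.85, with type I error 7.6%, 8.5% and 9.4%. Week 13 reverses direction, week 26 is no longer spared, and week 49 stays too liberal.

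**Dropout.** With 20% monotone dropout, the ratio for the arm difference at a visit is 0.97 to 1.01.

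**Binary outcomes.** A random-intercept logistic model was fitted to simulated null data with decaying latent correlation, 400 trials per setting:

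| Setting | Week 13 | Week 26 | Week 49 |
|---|---|---|---|
| 0.7 per 13 weeks, 240 per arm | 1.11 (2.8%) | 0.97 (6.2%) | 0.91 (7.0%) |
| 0.85 per 13 weeks | 1.05 (3.5%) | 0.97 (4.3%) | 0.88 (8.5%) |
| 0.7 per 13 weeks, 80 per arm, 65% suppressed | 1.10 (4.0%) | 0.99 (5.0%) | 0.87 (9.0%) |

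These are change contrasts. At-visit ratios were 0.97 to 1.01 throughout. Monte Carlo error is about ±0.07 per ratio, and a control run with equal correlation 0.5 gave change ratios of 0.90, 0.98 and 1.04, so single entries are imprecise. A separate set, with latent correlation falling from 0.8–0.9 to 0.4–0.5 and 160 or 480 participants, rejected 8.8% to 10.0% of null trials at week 49, with standard errors about 15% too small. All seven decaying settings point the same way at week 49.

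**The case against.** The strongest reply is that the problem needs four things together: an intercept-only participant effect, model-based standard errors, correlation that decays, and a test of change from baseline. The documents establish none of them outright. Much of this stands.

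- The text says random effect, not random intercept, and is silent on residual covariance and variance estimation. A reader might infer that the plan forces equal correlation. It does not: that is the natural reading of a single participant effect with nothing else stated, but it is still a reading.
- A reader might also infer that every week-49 comparison has standard errors that are too small and every week-13 comparison ones that are too large. This is not supported. Arm differences at a visit are essentially correct, and the sample size rests on a two-group comparison of proportions, not on change.
- The week-13 direction is not secure. Entry requires a raised ASSIST score or confirmed methamphetamine use, so baseline may correlate weakly with later visits, and the direction then reverses. Methamphetamine use is the only primary outcome with a week-13 time point. The binary results at week 13 are close to Monte Carlo error.
- The four-visit range does not carry over to outcomes that Table 1 schedules at two or three visits.

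What the reply does not remove is the week-49 result for change. It persists with three visits and with weak baseline correlation. It disappears if correlation does not decay at all over 49 weeks, or if the outcome has only two visits.

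**Conclusion.** The concern holds in conditional form. If the participant effect is a random intercept with model-based standard errors, and correlation falls with time, the intervention-by-time contrast of week 49 with baseline is anti-conservative. Over the assumed decay range, a nominal 5% test runs at about 9% to 14% for continuous outcomes with four visits and 7% to 10% with three. For binary outcomes the week-49 standard errors are roughly 10% to 15% too small, subject to appreciable simulation error. Every size rests on correlations that the documents do not give.

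No general statement about week 13 is warranted, and the planned sample size is untouched. This is an under-specified analysis that should be tightened because a primary time point is exposed and the remedy is cheap. It is not a flaw that invalidates the design.

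**What to change.** In Data analysis, To assess effectiveness:

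1. State for each primary outcome and time point whether the test is the arm difference at the visit or in change from baseline. State the link function and the visits that enter each model.
2. For continuous outcomes, use an unstructured within-participant covariance across the scheduled visits and keep the clinic random effect.
3. For binary outcomes, base intervals and p-values on robust (sandwich) standard errors. Cluster them by participant with clinic as a fixed effect, or by clinic with a small-sample correction for 20 clinics. Clustering by participant alone would ignore the clinic level. An independent participant-by-visit random effect is not a substitute, because it cannot be identified from one binary result per visit.

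The cost is a few sentences of plan text, a few more covariance parameters, and slightly noisier standard errors in the 200 HIV-positive participants. No extra data or participants are needed.

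### The planned model has no clinic-by-arm term, so if outcomes are correlated within the low-intensity group sessions, the standard error of the frontline contrast is too small

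*Combined protocol and SAP*

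**What the plan says.** All references are to the combined protocol and SAP.

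- **Model** (Data analysis, To assess effectiveness). Two random terms are listed: "The mixed-effects models will include a participant-level random effect to account for repeated observations of each participant", and "a clinic-level random effect to account for the nested nature within the clinics". There is no term for session group, counselor or clinic-by-arm.
- **Randomization** (Randomization and Interventions). "An investigator will stratify participants by HIV status and randomize them into two frontline interventions using REDCap". Individuals are randomized and clinic is not listed as a stratifier, so both arms are treated within the same clinics.
- **Frontline delivery** (Two frontline interventions). High intensity: "Participants in this arm receive contingency management with the escalating-and-reset schedule throughout 12 weeks", with no group sessions described. Low intensity has contingency management for six weeks, and then: "For the last six weeks, they attend weekly group education sessions".
- **Adaptive delivery** (Three adaptive strategies). Enhanced treatment 1: "Participants attend 12 weekly Matrix group counseling sessions facilitated by the clinic counselors". Enhanced treatment 2: "Participants receive the same Matrix intervention plus contingency management over 12 weeks". The section does not say whether the two arms share Matrix groups.
- **Staff** (Training and fidelity monitoring). In each clinic, "two counselors will run motivational interviewing, group education sessions and Matrix meetings".
- **Sample size** (Sample size determination). A plain two-group comparison of binary outcomes, with no mention of clustering or a design effect.

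**The concern.** People who attend the same sessions under the same counselors may come to have similar outcomes. That similarity arises after randomization, so randomizing individuals does not remove it. A clinic intercept is one number added to everyone in the clinic; it is common to both arms and largely cancels from the arm contrast. Similarity that exists only among a clinic's low-intensity participants does not cancel. It goes straight into the variance of the contrast, and the listed model has nowhere to put it.

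At stake are the confidence interval and type I error for high versus low intensity, the comparison for which the trial was sized. Methamphetamine use is the most exposed outcome, because it is a primary outcome analysed in participants of both HIV statuses, where clusters are largest.

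**Working it through.** **1. The plan's own figure.** From Sample size determination: 100 HIV-positive participants per group, 20% attrition (so 80 analysed), 80% power, 5% alpha (taken as two-sided), base rates of 60% to 70% for viral suppression and 80% to 90% for substance use. For 60% versus 80%, with mean proportion 0.7:

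z = (0.20 × √80 − 1.96 × √(2 × 0.7 × 0.3)) / √(0.6 × 0.4 + 0.8 × 0.2) = (1.789 − 1.270) / 0.632 = 0.82, so power is 79.4%.

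The smallest detectable difference at a base rate of 60% or 80% is 20.2 points. The stated 20 points is reproduced, without continuity correction and without any allowance for clustering.

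**2. Average cluster sizes, derived from the plan.**
- Combined sample: 600 / 20 clinics / 2 arms = 15 per clinic-arm; × 0.8 = 12.
- HIV-positive: 200 / 20 / 2 = 5; × 0.8 = 4.
- Enhanced arms, if half of the sample moves on (the minimum given under Modification of eligibility criteria): 300 / 20 / 2 = 7.5; × 0.8 = 6.

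**3. Assumptions.** The ICC (ρ) is not given; 0.01, 0.02 and 0.05 are used. The usual group size is not given; one group per clinic-arm is used, with groups of five as the milder case. Cluster sizes are taken as equal.

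**4. Frontline contrast.** Only one arm has groups, so the variance ratio is the average of 1 and the usual design effect:

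V = (1 + [1 + (m − 1)ρ]) / 2, and actual alpha = 2 × (1 − Φ(1.96 / √V)).

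Example, m = 12 and ρ = 0.05: design effect 1.55; V = 2.55 / 2 = 1.275; √V = 1.129; alpha = 2 × (1 − Φ(1.736)) = 8.3%.

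| Setting | V at ρ = 0.01 / 0.02 / 0.05 | Actual alpha |
|---|---|---|
| Combined, m = 12 | 1.055 / 1.11 / 1.275 | 5.6% / 6.3% / 8.3% |
| Combined, groups of 5 | 1.02 / 1.04 / 1.10 | 5.2% / 5.5% / 6.2% |
| HIV-positive, m = 4 | 1.015 / 1.03 / 1.075 | 5.2% / 5.3% / 5.9% |

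At ρ = 0, V = 1 and alpha is 5% in every row.

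**5. Enhanced 1 versus Enhanced 2.** If Matrix groups are formed by arm, both arms are clustered and V = 1 + (m − 1)ρ. With m = 6, V is 1.05 / 1.10 / 1.25 and alpha is 5.6% / 6.2% / 8.0%. If the arms share a group, the group effect is common to both and cancels.

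**6. Check by simulation.** A clinic-random-intercept model was simulated with a continuous outcome and 20 clinics.
- Frontline, m = 12: one set of runs gave 5.5%, 6.7% and 9.0% at ρ = 0.01, 0.02 and 0.05. Other sets gave 7.6% and 8.7% at ρ = 0.05.
- Frontline, groups of five: 5.4% to 6.6%.
- Frontline, HIV-positive, m = 4: 5.9% at ρ = 0.05 in one set, and up to about 6.6% in another.
- Enhanced arms, separate groups, m = 6: 6.2%, 6.4% and 8.7%.
- Enhanced arms, shared group: 5.3% at ρ = 0.05, within simulation error of 5%.
- A clinic-level analysis that allows clinic-by-arm variation (19 degrees of freedom) held type I error at 4.5% to 5.5%.

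**The case against.** The strongest reply is that the harm is conditional and may be slight. The documents report no group correlation. Group education covers only six of the 12 frontline weeks. During COVID-19 surges groups are limited to five or fewer, or replaced by individual sessions. Viral suppression is assessed only in the HIV-positive subset, where clusters are small. Viral suppression and HIV risk behaviors are primary at weeks 26 and 49, by which time responders have moved to text messages and non-responders have been re-randomized, so the frontline groups have dispersed. The calculation also uses one time point and a continuous outcome, whereas the plan has repeated measures and binary outcomes.

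Most of this stands, and it limits the size of the point. It does not remove it. The limit of five applies only during surges, and the usual size is not stated. Counselor differences between clinics could act on one arm more than the other even with small groups, and the plan itself provides for staff whose delivery drifts. Methamphetamine use is also primary at week 13, directly after the group sessions.

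A reader might infer two stronger conclusions that the documents do not support:
- **That the standard errors are too small as a matter of fact.** This needs a positive within-group correlation, which the documents neither give nor rule out.
- **That the enhanced-treatment comparison is equally at fault.** Both arms receive the same Matrix content from the same two counselors, and with about six or seven people per arm and clinic, joint groups are plausible. Joint groups give no inflation.

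**Conclusion.** The point holds in conditional form. The listed model cannot represent correlation that arises in one arm of a clinic, and the frontline stage has group sessions in one arm only. With an assumed ICC of 0.01 to 0.05 and one group of 12 per clinic-arm, the variance of the frontline contrast in the combined sample is about 5% to 28% larger than the model assumes, and a nominal 5% test runs at about 5.5% to 9%. The range is about 5% to 6% with groups of five, and slightly above 5% to about 6.6% in the HIV-positive subset. With no within-group correlation there is no error.

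For Enhanced 1 versus Enhanced 2 the range is about 6% to 9% if groups are formed by arm, and there is no inflation if they are shared. The plan leaves this open.

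A reader might also infer that the stated 20-point detectable difference is wrong. It is not, on its own inputs. In the HIV-positive subset an ICC of 0.05 would lower the power of a correctly sized test for 60% versus 80% from 79.4% to 76.4%.

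This is a modest, inexpensive improvement to the variance model and not a fatal flaw.

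**What to change.** - **Model.** For the frontline contrast, add a clinic-by-intervention random effect to the participant and clinic effects. Alternatively, keep the listed model and use clinic-level cluster-robust standard errors with a small-sample correction for 20 clinics. Name one of these as primary in the analysis section.
- **Enhanced arms.** State whether Matrix groups are shared or arm-specific. If arm-specific, apply the same term or correction to that contrast.
- **Fallback.** State in advance that the small-sample-corrected robust errors will be used if the added variance component cannot be estimated reliably. This is most likely in the HIV-positive subset.
- **Record.** Describe how groups are formed and log group membership, so that the correlation can be reported.

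The first change needs only clinic and arm, which the trial already collects. The cost is somewhat wider intervals (true standard error about 1.03 to 1.13 times the model's over the assumed range in the combined sample) and a variance component that 20 clinics may estimate imprecisely. Because the model has two intervention stages and time interactions, the wording must say which contrasts carry the added term.
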